9.3 Procedures for Reporting a Serious Adverse Event

Any serious adverse event occurring during the study period (beginning with informed consent/assent) and for at least 12 weeks after the last dose of study drug must be immediately reported but no later than 24 hours after learning of a serious adverse event. Serious adverse events must be reported to Allergan (or Agent of Allergan) as listed on the Allergan Study Contacts Sheet and recorded on the serious adverse event form. All patients with a serious adverse event must be followed up and the outcomes reported. The investigator must supply the sponsor and the IRB/IEC with any additional requested information (eg, autopsy reports and discharge summaries).

In the event of a serious adverse event, the investigator must:

1. Notify Allergan immediately by fax or email using the serious adverse event form (contact details can be found on page 1 of the serious adverse event form phone numbers and relevant Allergan personnel contacts are also on the front page of protocol.
2. Obtain and maintain in his/her files all pertinent medical records, information, and medical judgments from colleagues who assisted in the treatment and follow-up of the patient.
3. Provide Allergan with a complete, written description of the adverse event(s) on the serious adverse event form describing the event chronologically, including any treatment given (eg, medications administered, procedures performed) for the adverse event(s). Summarize relevant clinical information about the event: signs, symptoms, diagnosis, clinical course and relevant clinical laboratory tests, etc. Include any additional or alternative explanation(s) for the causality which includes a statement as to whether the event was or was not related to the use of the investigational drug.
4. Promptly inform the governing IRB/IEC of the serious adverse event as required by the IRB/IEC, local regulations, and the governing health authorities.

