## 2.3 Data Conventions

The following data conventions will be applied to all analyses:

- Only data with exceptions will be listed for conciseness. For example, the following would not be listed: normal findings for medical history and physical examination, pregnancy tests results for males or females when not applicable, etc.
- The level of significance used for all statistical tests will be 0.05, 2-sided, unless stated otherwise. P-values ≤0.050 will be considered as statistically significant.
- The type III sums of squares will be used for all analysis of covariance models (ANCOVA) and analysis of variance models (ANOVA).
- The variance for Kaplan-Meier estimates will be calculated using Greenwood's formula.
- Descriptive statistics for continuous variables will include the sample size (n), mean, standard deviation (SD), median, minimum (min), first quartile (Q1), third quartile (Q3), and maximum (max).
- Summary statistics for categorical variables will include the sample size (n), frequency count and percent.

- The Medical Dictionary for Regulatory Activities (MedDRA) dictionary will be used to code all adverse events (AEs) and medical history.
- World Health Organization Drug Dictionary Enhanced (WHO DDE) preferred name and MedDRA will be used to code all medications.
- Study duration from randomization/day 1 will be calculated as:  
$$\text{Study days} = \text{visit date} - \text{randomization/day 1 visit date} + 1.$$
- The Cycle duration for treatment X will be calculated as:  
$$\text{Study days} = \text{visit date} - \text{treatment X date} + 1.$$
- The algorithm presented in [Table 3](#), together with the rules below will be used to impute incomplete or missing dates for adverse events and medications as follows:
  - (a) AE start dates will be imputed as the minimum of the following:
    - initial imputed date, where target date = first study drug injection date.
    - complete end date
  - (b) Medication start dates will be imputed as the minimum of the following:
    - initial imputed date, where target date = first study drug injection date – 1.
    - complete end date
  - (c) AE and Medication end dates will be imputed as the minimum of the following:
    - initial imputed date, where target date = study exit date + 30.
    - Death date
- For each treatment cycle, AEs will be counted with onset date between the day when the study treatment is received and the day before the next treatment is received or exit day.

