## **6.2 Adverse Events**

AEs will be coded from the verbatim text into preferred term and the primary SOC by using the MedDRA dictionary. Events will be summarized by BOTOX treatment cycle.

A treatment-emergent adverse event (TEAE) for the study treatment period is an AE with onset after the initiation of study treatment or an AE with onset prior to study treatment that worsened in severity or became serious after the initiation of study treatment.

For a given treatment cycle, a TEAE is an AE with onset after the initiation of cycle treatment or an AE with onset prior to cycle treatment that worsened in severity or became serious after the initiation of cycle treatment.

An AE that stops during treatment cycle 1 and recurs in treatment cycle 2 is considered as a TEAE in treatment cycle 2 if it fulfills the TEAE definition above with respect to initiation of cycle 2 treatment.

The incidence of TEAEs will be summarized and presented for all events and will be tabulated by treatment group as follows:

- i. By relationship to treatment. Classified for all TEAEs and treatment-related TEAEs.
- ii. By descending order of frequency.
- iii. By primary SOC and preferred term. At each level of summarization (overall, primary SOC, and preferred term) a patient will be counted once if he/she reports 1 or more experiences at that level.
- iv. By primary SOC, preferred term and severity. For a given adverse event of a patient, if more than 1 severity grade was reported, the worst severity grade will be included in the tabulation. Statistical hypothesis tests will not be performed for this summary.

All treatment-related TEAEs (study drug-related, and injection procedure-related adverse events) will be presented. In addition, study drug-related and injection procedure-related AEs will be presented separately.

Treatment-related TEAEs will be analyzed by the same procedure outlined above (ii, iii, and iv). In addition, the number and percent of patients discontinued due to treatment-related TEAEs will also be tabulated by treatment group.

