All the summaries discussed above will be based on all AEs observed during the entire treatment cycle. Since the design of this study allows patients to request/receive retreatment from week 12 (day 84) onward, an additional summary showing the number and percentage of patients with TEAEs by preferred term and treatment group in descending order of incidence will be presented for the TEAE observed prior to or on day 84 after each injection cycle. This will allow for a comparison across dose groups for the same duration of time (ie, since patients can request retreatment from week 12 onwards, patients remain in a cycle for varying time periods). Therefore this analysis provides a more direct comparison across dose groups.

In addition, the number and percentage of patients who have a treatment-emergent UTI during the first 2 weeks (14 days), the first 12 weeks (84 days), and during the overall treatment cycle will be presented by the treatment received in each treatment cycle.

A patient listing will be generated for TEAEs, sorted by primary SOC, preferred term, relationship, and severity. In addition, the number and percent of patients discontinued due to TEAEs will also be tabulated by BOTOX treatment group for each BOTOX treatment cycle. A listing will also be generated for patients who discontinued due to TEAEs.

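### SAP 2.3 assigns adverse events to cycles by onset date alone, which conflicts with the SAP 6.2 rule that an event worsening after a cycle's treatment is a TEAE of that cycle

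*SAP*

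**What the plan says.** SAP 2.3 opens its list with "The following data conventions will be applied to all analyses". One bullet assigns events to cycles as follows: "AEs will be counted with onset date between the day when the study treatment is received and the day before the next treatment". In the last cycle the interval ends on exit day instead. Onset is the only date it uses.

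SAP 6.2 defines a cycle's TEAE more widely. Besides events that start after the cycle's treatment, it includes "an AE with onset prior to cycle treatment that worsened in severity or became serious after the initiation of cycle treatment". The whole-study definition has the same second part: "an AE with onset prior to study treatment that worsened in severity or became serious after the initiation of study treatment". In the severity table, "if more than 1 severity grade was reported, the worst severity grade will be included in the tabulation". The section adds: "All the summaries discussed above will be based on all AEs observed during the entire treatment cycle".

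SAP 6 presents safety results by cycle under the dose received in that cycle. SAP 6.3 tabulates serious events by cycle, and it limits them to a study treatment period whose end it does not define.

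On collection, protocol 9.1.1 records adverse events from consent onward. Protocol 9.3 sets a reporting duty for serious events that covers the study period and "for at least 12 weeks after the last dose of study drug must be immediately reported". Protocol 8.7 lets patients withdraw at any time and follows those who agree for at least 12 weeks after treatment.

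**The concern.** An event that begins before a treatment and worsens after it is one that 6.2 deliberately counts as treatment-emergent. By onset date, 2.3 does not place it in that cycle. Two competent programmers could therefore build different safety tables from the same data, each following the SAP.

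The cycle decides the dose column. SAP 1.1 lets the investigator keep or raise the dose at retreatment, never lower it. An event held in its onset cycle therefore stays under a dose equal to or lower than the one given before it worsened. In a dose comparison, an error that runs only one way matters more than random misplacement.

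The end of the last cycle raises a related question. If the cycle stops at exit day and a patient exits less than 12 weeks after the last dose, a serious event can be reportable under the protocol yet belong to no cycle.

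**Working it through.** The plan gives no figure to reproduce here. The check applies both rules to the same events.

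**Rules**
- Onset rule (SAP 2.3): count in cycle *k* if treatment day *k* ≤ onset ≤ day before treatment *k*+1, or exit day for the last cycle.
- TEAE rule (SAP 6.2): count in cycle *k* if onset falls in the cycle, or if onset precedes treatment *k* and the event worsens or becomes serious within the cycle.
- For serious events after exit, the comparison window is 12 × 7 = 84 days from the last treatment (protocol 9.3).

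**Illustrative dates (assumed):** treatments on days 1 and 120 and exit on day 300 for cases 1 to 4; one treatment on day 1 and exit on day 30 for case 5. Worsened events are assumed to keep their original onset date.

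| Case | Onset rule | TEAE rule / reporting window |
|---|---|---|
| 1. Onset in screening, worsens day 10 | no cycle | cycle 1 |
| 2. Onset day 100, worsens day 130 | cycle 1 only | cycles 1 and 2 |
| 3. Onset in screening, serious on day 130 | no cycle | cycle 2 |
| 4. New onset day 130 | cycle 2 | cycle 2 |
| 5. Exit day 30, serious event with onset day 50 | no cycle | cycle 1 (50 < 1 + 84 = 85) |

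Cases 1 and 3 drop out of every cycle table. Case 2 is missing from the cycle in which it worsened and, if the dose was raised at day 120, sits only under the lower dose. Case 4 shows that new events raise no conflict.

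The recurrence sentence in SAP 6.2 does not settle cases 1 to 3. It covers an event that stops and returns, not one that continues and worsens.

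**Reportable days after exit**, for case 5, by week of exit after the last dose (84 − 7 × week):
- week 2: 84 − 14 = 70 days
- week 6: 84 − 42 = 42 days
- week 10: 84 − 70 = 14 days
- week 12 or later: 0 days

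**Number of patients.** Protocol 4.1 plans for 10% dropout by week 12, or 108 × 0.10 = 10.8 patients. This is the only figure in the documents that bears on early exit. It is a planning rate for the first cycle and says nothing about how many serious events follow exit.

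**The case against.** The best defence is that 6.2 is the specific rule for the TEAE tables and 2.3 a general date convention, so a sensible programmer would follow 6.2. That is a possible reading. But 2.3 claims every analysis, and nothing in the SAP gives 6.2 precedence, so the conflict stands.

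The second defence is about data capture. If the eCRF opens a new record with a new onset date when an event worsens, the two rules agree. Neither document says how worsening is recorded. The reference in 6.2 to more than one reported grade fits one record with several grades, but also several reports of one term. This objection limits the size of the problem and stands as a condition on it.

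A reader might go further and infer that a grade reached in cycle 2 would be shown as severe in cycle 1, because the worst grade is tabulated. The documents do not establish that. The summaries are by cycle and rest on events observed during the cycle, and the worst-grade sentence does not say whether it looks across cycles.

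A reader might also infer that serious events of about 11 early leavers are lost. That is not supported either. No section places exit day before the protocol 8.7 follow-up. Protocol 5.5 exits patients over dose decisions only after at least 12 weeks, and protocol 4.5.1.1 does the same for pregnancy. A reporting duty is also not an analysis window, so its greater length is not in itself a contradiction. The figure of 11 is planned dropout, and SAP 15 records that recruitment was stopped, so 108 is itself only a plan.

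Finally, the events would not vanish. SAP 6.3 promises a listing of patients with serious events, 6.2 a listing of TEAEs, and SAP 15 puts pretreatment events in listings. What is at risk is their place in incidence by cycle and dose.

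**Conclusion.** The conflict between SAP 2.3 and 6.2 is real on the text and should be resolved before database lock. Its effect rests on one assumption, that a worsened event keeps its original onset date. On that assumption the onset rule omits the event from the cycle in which it worsened, and omits pretreatment events that worsen from all cycles. Under the planned dosing rule, any misplacement is to an equal or lower dose.

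The post-exit gap holds only if exit day comes before the 12-week safety follow-up, and then only for exits less than 12 weeks after the last treatment.

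Neither effect can be sized from the documents. Sample size, power and the efficacy analysis are untouched.

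**What to change.** Replace the SAP 2.3 bullet with:

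> An AE is counted in the cycle in which it starts, and in any later cycle in which it worsens in severity or becomes serious after that cycle's treatment, using the worst grade reached within that cycle. An AE that starts before treatment 1 is counted in every cycle in which it worsens or becomes serious. SAEs with onset after exit but within 84 days after the last treatment are counted in the last cycle, with a footnote that follow-up after exit may be incomplete.

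Pretreatment events must count in every such cycle, not only the first, because 6.2 judges each cycle on its own. The SAP should also say whether exit day precedes or follows the protocol 8.7 follow-up, how worsening is recorded in the eCRF, and where the study treatment period in 6.3 ends.

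The cost is SAP wording and programming, with no new data collection. There are two drawbacks. One event can appear in more than one cycle, so cycle counts will not add up to a study total. Ascertainment after exit is also unequal between patients, which the footnote discloses but does not remove.

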**Table 3 Initial Imputed Date Algorithm**

Available Year (YYYY)	Available Month (MM)			
	Missing	< Target Month	= Target Month	> Target Month
Missing	Target Date	—		
< Target Year	YYYY-12-31	YYYY-MM-LD		
= Target Year	Target Date	YYYY-MM-LD	Target Date	YYYY-MM-01
> Target Year	YYYY-01-01	YYYY-MM-01		

### 2.3.1 Diary Data Conventions

- For baseline and post-treatment visits, analyses will be based on the diary data collected over 2 consecutive days. For each day, the bladder diary will be used to collect wake time (time patients woke up to start the day), bedtime (time patients go to bed to sleep at night), urinary episodes (incontinence, urgency, catheterization, or voluntary void) during the daytime collection period, volume of each void over 1 daytime period, and presence/absence of nighttime urinary incontinence.
- A valid diary day is defined as a day where there are 1 or more urinary episodes of any type (incontinence, catheterization, or voluntary void) during the daytime collection period. In the case of patients who partially complete their diary, providing that at least 1 valid diary day out of 2 is available, the 2-day frequency of daytime urinary incontinence will be prorated with the value from the valid diary day, i.e. it is the average of the daytime urinary incontinence in the valid diary day multiplied by 2.
- If less than 1 diary day out of 2 has been completed, the frequency of daytime urinary incontinence will be set to missing.
- Missing daily average frequency of episodes of daytime urinary incontinence at baseline will be imputed using the median of all non-missing values at baseline within the same treatment dose group received for the first treatment (grouped to the nearest dose group based on the dose actually received). For scheduled visits up to week 12 after the first study treatment, missing daily average frequency of episodes of daytime urinary incontinence will be replaced using the last observation carried forward (LOCF) approach. Baseline values will not be carried forward. No imputation will be done for missing values on visits after the post-treatment 1 week 12 visit.

- For normalization of frequency of daytime urinary incontinence episodes in a given day to a 12-hour daytime period, the following algorithm will be used:
  - Apply visit window defined in Section 2.2 that uses days from treatment as reference.
  - Identify wake time and bedtime within the visit window. Daytime period (in hours) is determined by time between wake time and bedtime for that day.
  - Using the example below, 4 urinary incontinence episodes are recorded during the first daytime period of 16 hours (7:00am to 11:00pm), and 7 urinary incontinence episodes are recorded during the second daytime period of 14 hours (8:30am to 10:30pm).

On a given day, the number of daytime urinary incontinence episodes normalized to a 12-hour daytime period will be calculated by

$$\frac{12}{\text{daytime period}} \times \text{number of daytime urinary incontinence episodes ,}$$

which, in the example, adjusts to 3 ( $= 12/16 \times 4$ ) and 6 ( $= 12/14 \times 7$ ) normalized urinary incontinence episodes, respectively. The daily average frequency of daytime urinary incontinence episodes by the normalized daytime period in a given week visit will be 4.5 ( $= (3 + 6)/2$ ) in the example.

- If wake time is missing, the missing wake time will be imputed by either the first urinary episode time of any type recorded on that day or 7:00 am, whichever comes earlier. If bed time is missing, the missing time will be imputed by either the last urinary episode time of any type recorded on that day or 10:00 pm, whichever comes later.

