4.1 Number of Subjects

Approximately 108 patients will be randomized at approximately 35 to 45 sites in order to have an estimated 96 patients (32 per treatment group) based on an anticipated dropout rate of 10% by the primary timepoint of week 12 after treatment 1.

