### 1.1 Primary Study Objectives and Design

The primary objective is to evaluate the safety and efficacy for the treatment of urinary incontinence due to OAB in patients 12 to 17 years of age who have not been adequately managed with anticholinergic therapy.

Patients may participate in the study for 96 weeks following entry into the study and should have at least 12 weeks follow-up since the last treatment prior to exiting the study. Eligible patients are randomized to 1 of 3 treatment groups in a 1:1:1 ratio:

- 25 units (U) BOTOX (not to exceed 6 U/kg)
- 50 U BOTOX (not to exceed 6 U/kg)
- 100 U BOTOX (not to exceed 6 U/kg)

In order to ensure that an upper dosing limit of 6 U/kg is not exceeded, the actual dose administered will be adjusted based on the patient's weight if necessary.

Patients will be centrally randomized. In order to ensure balance across treatment groups, patients will be stratified by baseline daytime urinary urgency incontinence episodes (a total of  $\leq 6$  episodes or  $> 6$  episodes over the 2-day diary collection period).

Multiple treatments may be administered in this study. Doses received at subsequent retreatments will be determined by the investigator and based on the patient's response to the preceding blinded treatment. The investigator can elect to keep the dose the same or increase the dose compared with the preceding treatment. If it is deemed that a decrease in dose is warranted, the patient will be exited from the study. The first treatment will be administered on day 1.

All patients will be evaluated at scheduled clinic visits at weeks 2, 6, and 12 post-treatment, and thereafter at alternating telephone and clinic visits every 6 weeks until the patient qualifies for further retreatment or exits the study. Patients can request retreatment from week 12 since the preceding treatment. Once qualified for retreatment, the same visit schedule will be followed.

The primary efficacy measure is daytime urinary incontinence episodes, and the primary time point is week 12 after treatment 1.

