## 1.3 Sample Size

The sample size calculation for this study is determined empirically. A total of approximately 108 patients are to be enrolled for the study (32 per treatment group plus 10% attrition).

The following table displays the estimated differences between 100 U of BOTOX (maximum 6 U/kg) and 25 U of BOTOX (maximum 6 U/kg) in mean daily average frequency of daytime episodes of urinary incontinence change from baseline at week 12 for a range of common standard deviations (SDs). All calculations assume 32 patients per treatment group and a 2-sided test significance level of 0.05. The calculation was performed using the commercial software nQuery Advisor (procedure MTC0-1), version 6.01 (Statistical Solutions Ltd., Cork, Ireland), and the CI for the difference of 2 means based on normal distribution.

Standard Deviation	Distance From Mean to the Limit
2.0	0.980
2.5	1.225
3.0	1.470
3.5	1.715
4.0	1.960

Note: The ranges of the SDs are determined based on the values from Allergan's 2 pivotal phase 3 OAB studies, 191622-095 and 191622-520. The estimate of the SD for the 100-U BOTOX treatment group is 3.33 for Study 191622-095, 3.58 for Study 191622-520, and 3.46 for the 2 studies combined. The distance from mean to limit indicates how much the CI for the mean extends from the observed difference in means in either direction.

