### 5.2.1 Primary Analyses of Primary Efficacy Variables

The primary efficacy variable is the change from study baseline post treatment 1 in the daily average frequency of daytime urinary incontinence episodes (daytime is defined as the time between waking up to start the day and going to bed to sleep for the night).

Each daytime period recorded in the bladder diary will be normalized to represent a 12-hour period. The daily average frequency of daytime urinary incontinence episodes will be adjusted by the normalized daytime period.

For BOTOX treatment cycle 1, the treatment difference (least-squares [LS] mean difference) and 95% CI of the treatment difference in mean change from study baseline for 100 versus 25 U of BOTOX and 50 versus 25 U of BOTOX will be calculated. Pairwise comparisons of 100 versus 25 U of BOTOX and 50 versus 25 U of BOTOX up to week 12 posttreatment 1 will be evaluated using an ANCOVA model with study baseline value as covariate, and treatment group as factor. A hierarchical analysis strategy ([Lubsen and Kirwan, 2002](#)) to adjust for multiplicity will be used. In the order of (1) 100 versus 25 U of BOTOX, and (2) 50 versus 25 U of BOTOX, treatment group differences at week 12 will be tested at the 0.05 significance level in a fixed sequence fashion. Results of hypothesis testing for 50 versus 25 U of BOTOX will be considered for statistical significance only if the treatment difference for 100 versus 25 U of BOTOX is shown to be statistically significant. A similar analysis, without a hierarchal testing strategy, will be applied to other timepoints.

For each BOTOX treatment cycle, the mean raw value, mean change from study baseline, and 95% CIs for the arithmetic mean change from the study baseline will be summarized by study visit.

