### 5.2.2 Other Analyses of Primary Efficacy Variables

As a sensitivity analysis of the LOCF imputation method, mixed-effect model repeated measures analysis (MMRM) ([Mallinckrodt et al, 2001a](#) and [2001b](#)) will be conducted on the

primary efficacy variable with the observed data. The data will include all the observed cases up to and including the primary timepoint (week 12 after the first treatment). The unstructured variance-covariance structure will be used in the model. In contrast to LOCF that imputes missing values by carrying the last observed values forward, sensitivity analysis using MMRM allows for estimation of patient's missing response by using all the observed data and nonconstant correlations among the timepoints.

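### The primary week 12 dose comparison rests on LOCF-filled diaries, which can bias it modestly if dropout or response over time differs by dose; the MMRM already planned is the better primary analysis.

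*SAP*

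**What the plan says.** The primary hypothesis (SAP 5.2, protocol 7.3.1) concerns mean change from study baseline at week 12 after treatment 1. For missing diaries at scheduled visits up to then, SAP 2.3.1 states that "missing daily average frequency of episodes of daytime urinary incontinence will be replaced using the last observation carried forward (LOCF) approach". Protocol 7.2.1 has the same rule, and protocol 7.3.1 makes it part of the primary analysis. The model is an ANCOVA with baseline and treatment group (SAP 5.2.1). On its results, "treatment group differences at week 12 will be tested at the 0.05 significance level in a fixed sequence fashion": 100 U against 25 U first, then 50 U against 25 U only if the first is significant.

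SAP 5.2.2 already plans a second model, introduced with the words "As a sensitivity analysis of the LOCF imputation method, mixed-effect model repeated measures analysis (MMRM"). It uses observed data up to week 12 with an unstructured covariance. The SAP says that this model "allows for estimation of patient's missing response by using all the observed data", and contrasts that with LOCF. It names no fixed effects, gives no reason for keeping LOCF primary, and has no rule for the case where the two analyses disagree.

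Protocol 4.1 sets the number of patients "based on an anticipated dropout rate of 10% by the primary timepoint of week 12 after treatment 1". Neither document splits that rate by dose or by reason.

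**The concern.** The hypothesis is about week 12, but the analysed outcome is a mixture: week 12 diaries for those who stayed, and week 2 or week 6 diaries for those who left. Two mechanisms can separate a carried-forward value from the true week 12 value. A two-day diary is noisy, so a patient who leaves after a poor diary would tend to have a better one later. And the effect of a dose may change between weeks 2 and 12. If either error differs between doses, it enters the dose difference, its confidence interval and the p-value that opens or closes the second test. Filled values are also counted as observed, so the interval ignores the uncertainty in them.

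The plan already contains an analysis that needs weaker assumptions, but gives it no role in the decision.

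**Working it through.** **1. The plan's own figures.** SAP 1.3 says: "All calculations assume 32 patients per treatment group and a 2-sided test significance level of 0.05". The half-width of the interval is 1.96 × SD × √(2/32) = 0.49 × SD. For SD 2.0, 2.5, 3.0, 3.5 and 4.0 this gives 0.980, 1.225, 1.470, 1.715 and 1.960, as tabulated. At the pooled adult SD of 3.46 it is 1.70. For the total, 32/0.9 = 35.6, rounded up to 36, and 3 × 36 = 108, which matches "A total of approximately 108 patients are to be enrolled for the study (32 per treatment group plus 10% attrition".

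**2. Bias formula.** Let d be the proportion lost before week 12 in an arm. Let g be the mean, among those lost, of the carried-forward value minus the true week 12 value. The LOCF bias in the 100 U minus 25 U difference is

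d100 × g100 − d25 × g25.

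A negative result favours 100 U. If the two products are equal, the bias is zero.

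**3. Hand check.** Assume flat profiles, equal correlation ρ between visits, and dropouts whose last diary is on average 1 SD worse than their arm's mean. Then g = (1 − ρ) × 3.46, which is 2.08, 1.38 and 0.69 for ρ = 0.4, 0.6 and 0.8.
- 10% lost in each arm: 0.10g − 0.10g = 0.
- 5% lost at 100 U and 15% at 25 U: 0.05g − 0.15g = −0.10g, or −0.21, −0.14 and −0.07.
- The reverse split changes only the sign.

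**4. Simulation.** Three visits, 150,000 patients per arm, SD 3.46. Assumptions not in the documents: ρ from 0.4 to 0.8; 30% of dropouts leave after week 2 and 70% after week 6; the odds of leaving rise with a poor last response, except where stated. Rejection rates are normal approximations at 36 per arm, where SE = 3.46 × √(2/36) = 0.816. The baseline covariate was not simulated.

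| Scenario (100 U / 25 U) | LOCF bias, episodes/day | Effect on the test |
|---|---|---|
| 10% / 10%, flat | 0.00 | type I error 0.050 |
| 5% / 15%, flat | −0.08 to −0.23 | type I error 0.051 to 0.059; at a true difference of −1.5, rejection 49% to 57% instead of 45% |
| 10% random / 10% response-related, flat | −0.09 to −0.27 | type I error 0.051 to 0.063 |
| 10% / 10%, effect of 25 U wanes, true difference −1.5 | about +0.065 | rejection 42% instead of 45% |

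The waning result is about the same when dropout is fully random. The MMRM-type estimate was within 0.01 of the truth in every row.

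**5. Unequal rates need no dose-specific mechanism.** A separate run (200,000 per arm, ρ 0.4 and 0.6) applied one poor-response rule to both arms, with 10% lost overall after week 6 and a true difference of 1.5. The rule removed about 13% at 25 U and 7% at 100 U, simply because 100 U worked better. The bias was −0.08 to −0.09; 0.09/1.5 = 6%. Under no difference, the common rule gave no bias.

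**6. Size in context.** The largest value, 0.27, is 0.27/0.816 = 0.33 SE, or 0.27/1.70 = 16% of the planned half-width. No power target is stated. At 32 per group, SE = 3.46 × 0.25 = 0.865, and power for an illustrative difference of 1.5 is Φ(1.5/0.865 − 1.96) = 41%. A borderline first step is therefore plausible.

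**7. Where MMRM fails.** With 5% / 15% dropout that depends on the unseen week 12 value, the MMRM bias was +0.16 to +0.35 and the LOCF bias +0.07 to +0.21.

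**The case against.** The strongest reply is that the design limits early, response-related loss. Each cycle is a single injection, so there is no ongoing treatment to stop. Retreatment can be requested only from week 12 (protocol 5.10.1). Exits over dosing come after at least 12 weeks of follow-up (protocol 5.5). Patients who withdraw but agree to follow-up are followed for at least 12 weeks, and an early exit triggers exit assessments (protocol 8.7), which include the diary (protocol Table 1). The week 12 window is Day 65 to Day 127 (SAP Table 2), so an exit diary from Day 65 onward counts as observed. This stands and lowers the likely size, but it does not cover patients who leave before Day 65 or refuse follow-up.

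The reply can add that MMRM is already pre-specified, so readers will see both results. They will, but only the LOCF result decides the sequence, and nothing says what follows if the two disagree.

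It is also true that the unequal splits are assumptions, that MMRM is not better in every case, and that recruitment was stopped early (SAP 15). With smaller groups the SE grows and the same bias is a smaller share of it. All three points stand.

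**Conclusion.** The concern holds as a cheap improvement. LOCF can bias both dose contrasts, by about 0 to 0.27 episodes per day at the planned 10% overall dropout and SD 3.46, with type I error at most about 0.063. These figures were computed for 100 U against 25 U; the same formula applies to 50 U against 25 U. They rest on the assumed correlations, dropout splits and dropout mechanisms in the working.

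A reader might infer three stronger things that the documents do not support:
- **Any response-related dropout biases the dose difference.** It does not: equal rates with flat profiles cancel, and unequal random dropout with flat profiles does no harm because g = 0. The documents give one overall rate, with no sign of a difference by dose.
- **LOCF flatters 100 U.** The direction is open. It favours 100 U if 25 U loses more poor responders, and works against 100 U if the split is reversed or if 25 U wanes.
- **MMRM cures the problem.** It does so only if missingness depends on observed data.

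That last limit does not make LOCF the better default, because LOCF needs stronger assumptions and the plan offers no argument for it.

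**What to change.** Before unblinding, make the MMRM of SAP 5.2.2 the primary analysis for the fixed-sequence week 12 contrasts, 100 U against 25 U and then 50 U against 25 U. Specify it fully: observed, non-imputed diaries at weeks 2, 6 and 12; baseline, treatment, visit, treatment-by-visit and baseline-by-visit terms; unstructured covariance. Keep the LOCF ANCOVA as the sensitivity analysis and state how a disagreement will be read.

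Record the change in SAP 13, which now says that there are no deviations from the protocol. The same entry should settle a related mismatch: when every post-treatment diary is missing, protocol 7.2.1 carries the baseline value forward and SAP 2.3.1 does not. It should also note that the sensitivity analyses in protocol 7.4 (per-protocol population and median imputation) do not include MMRM.

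The cost is mainly SAP wording, since both models are already planned. There are three downsides. The primary method would depart from protocol 7.2.1 and 7.3.1, so it must be declared before unblinding. The interval may be slightly wider, because filled values no longer count as data. And MMRM can do worse than LOCF if dropout depends on the unseen week 12 value.
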